Boehringer
Ingelheim

Clinical Trial Protocol

Document Number:		c23806995-04
EudraCT No. EU Trial No.	N/A	
BI Trial No.	1368-0032	
BI Investigational Medicinal Product(s)	BI 655130	
Title	Phase IIa multicentre, randomized, double-blind, placebo-controlled, study to evaluate the safety, tolerability and efficacy of treatment with BI 655130 in adult patients with moderate to severe atopic dermatitis	
Lay Title	A study in patients with atopic eczema to test how effective BI 655130 is and how well it is tolerated	
Clinical Phase	Phase IIa	
Clinical Trial Leader	[REDACTED]	
	Tel: [REDACTED]	Fax: [REDACTED]
Coordinating Investigator	N/A	
Status	Final Protocol (based on Global Amendment 03)	
Version and Date	Version: 4.0	Date: 12 Feb 2020
Page 1 of 85		
Proprietary confidential information. © 2020 Boehringer Ingelheim International GmbH or one or more of its affiliated companies. All rights reserved. This document may not - in full or in part - be passed on, reproduced, published or otherwise used without prior written permission.		

CLINICAL TRIAL PROTOCOL SYNOPSIS

Company name	Boehringer Ingelheim
Protocol date	05 Nov 2018
Revision date	12 Feb 2020
BI trial number	1368-0032
Title of trial	Phase IIa, multicentre, randomized, double-blind, placebo-controlled, study to evaluate the safety, tolerability and efficacy of treatment with BI 655130 in adult patients with moderate to severe atopic dermatitis
Coordinating Investigator	N/A
Trial site(s)	Multi-centre trial
Clinical phase	IIa
Trial rationale	Although the pre-clinical data and rationale for the use of an IL-36R antagonist in atopic dermatitis (AD) are strong, there are no data on the use of an IL-36 receptor antagonist in patients with AD. Thus, a small proof of clinical concept study is planned to assess safety, tolerability and efficacy in patients with moderate to severe AD.
Trial objective(s)	The primary objectives of this trial are to investigate the safety, tolerability and efficacy of BI 655130 in adult patients with moderate to severe atopic dermatitis following repeated intravenous administrations of 600 mg compared to placebo.
Trial endpoints	Primary endpoint 
Percentage change from baseline in EASI at Week 16 Secondary endpoint 
Number of patients with drug related AEsAbsolute and percentage change from baseline in EASI at Week 4Proportion of patients with a 50% improvement from baseline in EASI (EASI50) at Week 4 and 16Proportion of patients with a 75% improvement from baseline in EASI (EASI75) at Week 4 and 16Change from baseline in SCORAD at Week 4 and 16Proportion of patients achieving at least a 2-grade reduction from baseline to clear (0) or almost clear (1) in IGA at Week 4 and 16
Trial design	Double-blind, randomised, placebo-controlled comparison of two groups over 16 weeks
Total number of patients randomised	Approximately 45 patients will be entered in the study
Number of patients on each treatment	30 patients in the active group 15 patients in the placebo group
Diagnosis	Adult patients with moderate to severe atopic dermatitis

Main in- and exclusion criteria	
Inclusion Criteria (for complete list refer to Section 3.3.2)
 
• Male or female patients, 18 to 75 years of age at screening• Diagnosis of atopic dermatitis for at least 1 year• Moderate to severe atopic dermatitis defined as:
○ At least 10% Body Surface Area (BSA) of atopic dermatitis involvement at screening and baseline○ Eczema Area and Severity Index (EASI) of at least 12 at screening and at least 16 at baseline,○ Investigator Global Assessment (IGA) of at least 3 at screening and baseline• Documented history of inadequate response to topical corticosteroid as judged by the investigator• Willing to use a standard emollient for the duration of the study• Women of childbearing potential (WOCBP)¹ must be ready and able to use highly effective methods of birth control per International Council on Harmonization (ICH) M3 (R2) that result in a low failure rate of less than 1% per year when used consistently and correctly. A list of contraception methods meeting these criteria is provided in the patient information. 
Exclusion Criteria (for complete list refer to Section 3.3.3)
 
• Use of topical corticosteroids or other agents for atopic dermatitis within 7 days prior to first dose of trial treatment.• Use of systemic corticosteroids or other agents for atopic dermatitis within 4 weeks prior to first dose of trial treatment (for more details refer to Table 4.2.3.1: 1)• Women who are pregnant, nursing, or who plan to become pregnant while in the trial.• Any documented active or suspected malignancy or history of malignancy within 5 years prior to the screening visit, except appropriately treated basal cell carcinoma of the skin, squamous cell carcinoma of the skin or in situ carcinoma of uterine cervix. Use of any restricted medication as specified in Table 4.2.3.1: 1 or any drug considered likely to interfere with the safe conduct of the study, as assessed by the investigator.• History of allergy/hypersensitivity to the systemically
---------------------------------	--

¹ A woman is considered of childbearing potential (WOCBP), i.e. fertile, following menarche and until becoming post-menopausal unless permanently sterile. Permanent sterilisation methods include hysterectomy, bilateral salpingectomy and bilateral oophorectomy. Tubal ligation is NOT a method of permanent sterilisation. A postmenopausal state is defined as no menses for 12 months without an alternative medical cause.

Proprietary confidential information © 2020 Boehringer Ingelheim International GmbH or one or more of its affiliated companies

	
administered trial medication agent or its excipients.
 
• Active systemic infections (Fungal and bacterial disease) during the last 2 weeks prior to first drug administration, per investigator assessment.• Relevant chronic or acute infections (exception: common cold) including human immunodeficiency virus (HIV) or viral hepatitis. A patient can be re-screened if the patient was treated and is cured from the acute infection.• Active or Latent TB:
• Patients with active tuberculosis are excluded.• Patients with a positive QuantiFERON TB test during screening are excluded, unless:
○ Patient had previous diagnosis of active or latent TB and has completed appropriate treatment per local practice/guidelines within the last 3 years and at least 6 months before first administration of trial medication under this protocol (patients may be re-screened once to meet this criterion)○ Patients with suspected false positive or indeterminate QuantiFERON TB result may be re-tested once○ If QuantiFERON TB test result is not available or providing indeterminate results after repeat testing: A tuberculin skin test reaction $\geq 10\text{mm}$ ($\geq 5\text{mm}$ if receiving $\geq 15\text{mg/d}$ prednisone or its equivalent) is considered positive.• Evidence of a current or previous disease, medical condition other than atopic dermatitis, surgical procedure, psychiatric or social problems, medical examination finding, or laboratory value at screening outside the reference range that in the opinion of the investigator is clinically significant and would make the study participant unreliable to adhere to the protocol, comply with all study visits/procedures or to complete the trial, compromise the safety of the patient or compromise the quality of the data.• Major surgery (major according to the investigator) performed within 12 weeks prior to first study drug administration or planned during the study (e.g. hip replacement, aneurysm removal, stomach ligation).• Severe, progressive, or uncontrolled hepatic disease, defined as >3-fold Upper Limit of Normal (ULN) elevation in AST or ALT or alkaline phosphatase, or >2-fold ULN elevation in total bilirubin.
Test product(s)	BI 655130

Proprietary confidential information © 2020 Boehringer Ingelheim International GmbH or one or more of its affiliated companies

dose	600 mg every 4 weeks
method and route of administration	Intravenous (i.v.)
Comparator product(s)	Placebo
dose	Matching placebo
method and route of administration	Intravenous (i.v.)
Duration of treatment	Up to 32 weeks
Statistical methods	
Restricted maximum likelihood estimation based on a mixed-effect model for repeated measures analysis will be used to obtain adjusted means for the treatment effects of the primary endpoint percent change in EASI Score. This model will include discrete fixed effects for treatment at each visit and stratification factor Asian/Non-Asian, and continuous fixed effects for baseline at each visit. The primary treatment comparisons will be the contrast between treatments at Week 16.
 
To compare proportion of patients reaching EASI 50 or 75, or having IGA 0 and 1, the Cochran-Mantel-Haenszel test will be used.
 
Safety data will be presented using descriptive methods.
 
An interim analysis will be conducted when 75% of the patients have completed at least 4 weeks of treatment.

Proprietary confidential information © 2020 Boehringer Ingelheim International GmbH or one or more of its affiliated companies

FLOW CHART
Randomised Treatment Period

Trial Periods		Screening											
Visit		1	2 ^{1*}	3	4	5	6	7 ¹⁷ Re-allocation	8	9	10 (EoS for R) ²	11 (EoS) / FU1 (NR) ^{3,18}	End of Study Safety Phone Call (NR) ²⁰
Day	-28 to -7	1	15	29	57	85	113		141	169	197	228 - 309	309
Week	-4 to -1		2	4	8	12	16		20	24	28	32 - 44	44
Time window for visits			±3 days	±3 days	±3 days	±3 days	±3 days		±3 days	±3 days	±3 days	±3 days	+/- 3 days
Screening/baseline													
Informed consent for main study	X												
Informed consent for PGx Sampling	X												
Demographics	X												
Smoking History	X												
Medical history	X												
Review of in-/exclusion criteria	X	X											
Randomisation		X											
Physician and Patient Assessments													
Investigator Global Assessment (IGA) ¹⁷	X	X	X	X	X	X	X		X	X	X	X	
EASI ¹⁷	X	X	X	X	X	X	X		X	X	X	X	
SCORAD ¹⁷	X ¹⁹ (BSA only)	X	X	X	X	X	X		X	X	X	X	
DLQI ¹⁷		X	X	X	X	X	X		X	X	X	X	
All AEs/SAEs/AESIs**	X	X	X	X	X	X	X		X	X	X	X	X
Treatment													
Administer trial drugs		X		X	X	X	X ¹⁶	X ¹⁶	X ¹⁶	X ¹⁶			
Concomitant therapy	X	X	X	X	X	X	X		X	X	X	X	X
Treatment Re-allocation							X						
End of Study Completion Call in IRT											X (R)	X ²² (NR)	X ²² (NR)
Safety													
Physical examination ⁴		X ^C	X ^T	X ^T	X ^T	X ^T	X ^T	X ^C	X ^T	X ^T	X ^{C,T}	X ^C	

Clinical Trial Protocol

Page 7 of 85

Proprietary confidential information © 2020 Boehringer Ingelheim International GmbH or one or more of its affiliated companies

Trial Periods	Screening	1	2 ^{1*}	3	4	5	6	7 ¹⁷ Re-allocation	8	9	10 (EoS for R) ²	11 End of Study (EoS)/FU1 (NR) ^{3,18}	End of Study Safety Phone Call (NR) ²⁰
Visit													
Day	-28 to -7	1	15	29	57	85	113	141	169	197	228 - 309	309	
Week	-4 to -1		2	4	8	12	16	20	24	28	32 - 44	44	
Time window for visits			±3 days	±3 days	±3 days	±3 days	±3 days	±3 days	±3 days	±3 days	±3 days	±3 days	+/ - 3 days
Vital signs ⁵	X	X	X	X	X	X	X	X	X	X	X	X	
Safety Laboratory tests (blood and urine) ⁶	X	X	X	X	X	X	X	X	X	X	X	X	
Pregnancy testing ⁷	X ⁸	X ^{U, (S)}		X ^{U, (S)}	X ^{U, (S)}	X ^{U, (S)}	X ^{U, (S)}	X ^{U, (S)}	X ²¹				
12 lead-ECG (local) ⁸	X	X	X	X	X	X	X	X	X	X	X	X	
Infection Testing ⁹	X										X	X	
Biomarker and PK sampling													
Skin Biopsies -Lesional (L) and non-lesional (NL) ¹⁰			X (L;NL)		X (L)		X (L)				X(L optional)	X(L optional)	
Photographs of skin lesion ¹¹			X		X	X	X						
Skin Tape stripping ¹²			X (L;NL)		X(L)		X(L)				X (L optional)	X (L optional)	
ADA/Nab ¹³			X	X	X	X	X	X	X	X	X	X	
PK Sampling ¹³			X	X	X	X	X	X	X	X	X	X	
Blood sample for RNA sequencing ¹³			X		X	X	X						
Blood sample for DNA resequencing ¹³			X										
Microbiome sample for 16S sequencing ¹⁴			X (L;NL)		X (L;NL)		X (L;NL)						
Blood sample – soluble protein ¹³ biomarker			X		X	X	X	X	X	X	X	X	
Blood sample – Optional PGx Sampling ¹⁵			X ¹⁵										

ADA, anti-drug antibody; AE, adverse events; AESI, adverse event of special interest; C, complete physical examination; DLQI, dermatology life quality index; EASI, Eczema Area and Severity Index; ECG, electrocardiogram; EOS, End of Study; L, lesional; PGx, pharmacogenomics; NL, non lesional; PK, pharmacokinetic; SAE, serious adverse event; SCORAD, SCORing of Atopic Dermatitis; T, targeted physical examination; TB, tuberculosis

Proprietary confidential information © 2020 Boehringer Ingelheim International GmbH or one or more of its affiliated companies

(*) Day of Randomisation / Day of first intake of randomised medication = Day 1.

(**) After the individual patient's end of the trial the investigator should report only any occurrence of cancer, related SAEs and related AESIs of which the investigator may become aware of and only via the SAE form. Please refer to Section [5.2.5.2](#).

1- Initiation of randomized treatment at Visit 2 can only begin if the patient meets the criteria for Initiation of Treatment. Please refer to Sections [3.3.2](#) and [3.3.3](#).

2- At Visit 10, Non- Responders (NR) will receive their last study drug administration and Responders (R) will have their End of Study (EoS) visit.

3- Should a patient prematurely discontinue before their scheduled EoS every effort should be made to keep the patient in the trial and complete all of the remaining study visits or at a minimum an early EoS visit. Patients who prematurely discontinue before V7/Wk16 are considered Non-Responders.

4- C = Complete Physical Examination (PE) includes general appearance as well as evaluation of all organ systems; T = Targeted physical examination includes evaluation of organ systems associated with AE(s) symptoms or laboratory abnormalities. At Visit 10 complete physical examination will be performed for Responders (EOS), targeted physical examination will be performed for Non-Responders. Please refer to Section [5.2.1](#).

5- Vital signs will be assessed at predose, at approximately 5 minutes after the end of infusion, and 60 mins after the end of infusion at visits with i.v. administration.

6- Safety laboratory tests include clinical chemistry, haematology, coagulation, and urinalysis, and will be performed centrally. Local Labs may be used for dosing decisions prior to i.v. administration. Please refer to Section [5.2.3](#).

7- Only applicable for women of childbearing potential. S – serum pregnancy test (performed at screening). U – urine pregnancy tests will be performed at all other visits indicated in the [Flow chart](#). Urine pregnancy testing should be done prior to administration of study drug. Study drug should only be administered in case of a negative test result. (S) - in case of a positive urine pregnancy test, a serum pregnancy test will be done. Please refer to Section [5.2.5.2](#).

8- ECG measurements should always precede blood sampling and drug administration. Clinically significant abnormal findings should be reported as AEs in the eCRF.

9- Infection testing includes tuberculosis, hepatitis B, hepatitis C, and HIV assessments. Please refer to Table [5.2.3: 1](#). For the EoS visit only tuberculosis and hepatitis B testing will be performed. For Responders the Infection testing will be conducted at V10 (Week28) which corresponds to their EoS. For Non Responders the Infection testing will be conducted at V11.

10- One (1) lesional (L) and One (1) non-lesional (NL) biopsy will be collected at V2 (baseline), One (1) lesional (L) biopsy will be collected at V4 (Week 4) and at V7 (Week 16). One (1) optional lesional (L) will be collected at EoS (V10 for Responders or V11 for Non-Responders). Each skin biopsy of 4.5 mm punch (split into half for IHC and RNASeq) should be collected prior to trial drug infusion.

11- Photographs of skin lesions are to precede skin biopsies and study drug administration. Please refer to Section [5.6](#).

12- Skin tape stripping samples will be collected as close as possible to the site of the skin biopsy and at the same timepoint. Skin tape stripping samples must be taken before biopsies are taken and before trial drug infusion. One (1) L and one (1) NL at V2; one (1) L at V4 (Week 4) and V7 (Week 16); and one (1) optional lesional (L) at EoS(V10 for Responders or V11 for Non-Responders).

13- pre dose PK and ADA and Nab samples will be collected within 2 hour period prior to infusion. In addition, all biomarkers samples will be collected prior to trial drug infusion. Please refer to Section [5.3](#).

14- Microbiome samples must be taken before biopsies are taken and before trial drug infusion.

15- Deoxyribonucleic acid (DNA) banking sample is optional. Participating patients are required to give informed consent specifically for this banking. Blood sample will be collected in a PAX-gene Blood DNA tube at day 1 (Visit 2). If not possible at Visit 2, this sample may also be collected during a later visit. The DNA banking sample must be collected prior to infusion of the trial drug infusion.

16- At V7 (Week 16) all patients will be evaluated with the EASI score. Non-responders will be re-allocated to receive BI open label trial drug from V7 (Week 16) onward until V10 (Week 28). Responders will be re-assigned to no treatment from V7 (Week 16) onward until V10 (Week 28) but will be expected to come to all visits.

Proprietary confidential information © 2020 Boehringer Ingelheim International GmbH or one or more of its affiliated companies

17- All assessments must be done prior to trial drug infusion. The questionnaires completed by patients should be done first before the investigator assessments. Please refer to Section [6.2](#).

18- For Responders (R) the EoS visit must be completed 16 weeks after last treatment, which is at the latest at Week 28 (V10). Responders (R) may complete EOS at any point after V7 (Week 16) if the patient drops to an EASI 50 score prior to the planned EOS. For Non Responder (NR) patients who have achieved EASI 50 and plan to participate in the extension trial, the EoS visit will be completed no earlier than Week 32. Non Responder patients not participating in the extension trial will complete a V11/FU1 visit between Week 32-44. If a patient should discontinue treatment prematurely every effort should be made to keep the patient in the trial and complete all of the remaining study visits or at a minimum an early EoS visit 16 weeks after last treatment.

[figure not shown]
19- At V1 (Screening) BSA will be assessed for eligibility. From V2 (baseline) onward BSA will be completed as part of SCORAD assessment.

20- Only Non-Responders not participating in the open label extension trial must complete an End of Study Safety Phone Call. V11 and End of Study Safety Phone call can occur on the same day only if the Residual Effect Period (16 weeks after last trial drug infusion) has been reached (WK44). The phone call cannot be performed before the V11.

21- Patients will be asked about their pregnancy status at the End of Study Safety Phone Call.

22- For Non-Responders participating in the open label extension trial, End of Study completion IRT call is registered at V11 as the End of Study Safety Phone Call is not required. For Non-Responders not participating in the open label extension trial, End of Study completion IRT call is registered only at End of Study Safety Phone Call (WK44). V11 is not registered in IRT.

TABLE OF CONTENTS

TITLE PAGE	1
CLINICAL TRIAL PROTOCOL SYNOPSIS	2
FLOW CHART	6
TABLE OF CONTENTS	10
ABBREVIATIONS	13
1. INTRODUCTION.....	16
1.1 MEDICAL BACKGROUND	16
1.2 DRUG PROFILE	17
1.2.1 Mode of Action	17
1.2.2 Nonclinical pharmacology.....	17
1.2.3 Clinical experience	18
1.3 RATIONALE FOR PERFORMING THE TRIAL	20
1.4 BENEFIT - RISK ASSESSMENT.....	20
2. TRIAL OBJECTIVES AND ENDPOINTS.....	22
2.1 MAIN OBJECTIVES, PRIMARY AND SECONDARY ENDPOINTS.....	22
2.1.1 Main objectives.....	22
2.1.2 Primary endpoint	22
2.1.3 Secondary endpoint(s)	22
	
3. DESCRIPTION OF DESIGN AND TRIAL POPULATION	24
3.1 OVERALL TRIAL DESIGN AND PLAN	24
3.2 DISCUSSION OF TRIAL DESIGN, INCLUDING THE CHOICE OF CONTROL GROUP(S)	25
3.3 SELECTION OF TRIAL POPULATION	25

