5.2.5.2 Adverse event collection and reporting

AE Collection

The investigator shall maintain and keep detailed records of all AEs in the patient files.

The following must be collected and documented on the appropriate CRF(s) by the investigator:

- From signing the informed consent onwards until the individual patient's end of trial:
 - all AEs (serious and non-serious) and all AESIs
- After the individual patient's end of trial:
the investigator does not need to actively monitor the patient for new AEs but should only report any occurrence of cancer and related SAEs and related AESIs of which the investigator may become aware of by any means of communication, e.g. phone call.
Those AEs should however not be reported in the CRF.

AE reporting to the sponsor and timelines

The investigator must report SAEs, AESIs, and non-serious AEs which are relevant for the reported SAE or AESI, on the BI SAE form immediately (within 24 hours) to the sponsor's unique entry point (country specific reporting process will be provided in the ISF). The same timeline applies if follow-up information becomes available. In specific occasions, the investigator could inform the sponsor upfront via telephone. This does not replace the requirement to complete and send the BI SAE form.

With receipt of any further information to these events, a follow-up SAE form has to be provided. For follow-up information the same rules and timeline apply as for initial information.

Information required

For each AE, the investigator should provide the information requested on the appropriate eCRF pages and, if applicable, the BI SAE form. The investigator should determine the causal relationship to the trial medication.

The following should also be recorded as an (S)AE in the CRF and, if applicable, BI SAE form:

- Worsening of the underlying disease or of other pre-existing conditions.
- Changes in vital signs, ECG, physical examination and laboratory test results, if they are judged clinically relevant by the investigator.

If such abnormalities already pre-exist prior to trial inclusion they will be considered as baseline conditions and should be collected in the eCRF only. All (S)AEs, including those persisting after a patient's end of trial, must be followed up until they have resolved, have been assessed as "chronic" or "stable", or no further information can be obtained.

Pregnancy

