6.2.2 Randomization Visit and Treatment Visits

Patients will be randomized to receive 600 mg BI 655130 or placebo in a 2:1 randomisation ratio (2:1) at Visit 2. Patients will be stratified according to race i.e Asian vs non-Asian.

The first study drug administration is at Visit 2 (Day 1). Thereafter, patients will receive blinded trial drug at V4, V5 and V6. At V7 patients will be evaluated with EASI score and responders will be re-assigned to no treatment whereas non-responders will be re-assigned to BI 655130 600 mg. The re-assignment will be un-blinded.

For information pertaining to PK, ADA, Nab and biomarkers, see Sections [5.3](#) and [5.4](#). Fasting is not required for blood sampling. For information pertaining to laboratory tests, ECG, vital signs, and physical examination, see Sections [5.2.1](#) to [5.2.5](#).

DNA banking is optional and is only to be done for patients who have provided informed consent for this specific procedure.

Skin lesion photographs will be taken at all visits on site and are to be taken prior to any skin biopsies or study drug administration.

At Visit 1, patients will be provided with emollient and instructions on how to apply. Emollient will be provided to each patient as required for the duration of the study.

Study drug allocation via the IRT system and administration of study drug should be the last activity at Visit 2 with the exception of post dose vital signs assessments.

For women of child-bearing potential, pregnancy testing will be done as specified in the [Flow Chart](#). The patient will also be asked about their pregnancy status at the End of Study Safety Phone Call.

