7.3.4 Safety analyses

Adverse events will be coded using the Medical Dictionary for Drug Regulatory Activities (MedDRA). Standard BI summary tables and listings will be produced. All adverse events with an onset between start of treatment and end of the residual effect period (REP), a period of 16 weeks after the last dose of trial medication, will be assigned to the on-treatment period for evaluation.

All treated patients will be included in the safety analysis. In general, safety analyses will be descriptive in nature and will be based on BI standards. No hypothesis testing is planned.

Statistical analysis and reporting of adverse events will concentrate on treatment-emergent adverse events, i.e. all adverse events occurring between start of treatment and end of the REP. Adverse events that start before first drug intake and deteriorate under treatment will also be considered as 'treatment-emergent'.

[figure not shown]
Frequency, severity, and causal relationship of adverse events will be tabulated by system organ class and preferred term after coding according to the current version of the Medical Dictionary for Drug Regulatory Activities (MedDRA) at database lock.

[figure not shown]
Laboratory data will be analysed both quantitatively as well as qualitatively. The latter will be done via comparison of laboratory data to their reference ranges. Values outside the reference range as well as values defined as clinically relevant will be summarised. Treatment groups will be compared descriptively with regard to distribution parameters as well as with regard to frequency and percentage of patients with abnormal values or clinically relevant abnormal values.

Vital signs, physical examinations, or other safety-relevant data observed at screening, baseline, during the course of the trial and at the end-of-trial evaluation will be assessed with regard to possible changes compared to findings before start of treatment.

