6. GENERAL ANALYSIS DEFINITIONS

6.1 TREATMENTS

For basic study information on the treatment to be administered, assignment to treatment, and selection of dose, cf. Section 4 of the CTP.

In the blinded treatment phase, all patients will receive either intravenous doses of 600mg of BI 655130 solution for infusion (at weeks 0, 4, 8, and 12), or Placebo.

At Week 16, all patients will be evaluated with the EASI Score. Non-responders (EASI < 75) will be re-allocated to receive BI open label trial drug from Week 16 through Week 28; they will be followed until Week 44. Responders (EASI >= 75) will be re-assigned to receive no further trial treatment but will be expected to come to all visits up to Week 28, when EOS visit is planned.

The following trial periods/phases are defined:

Table 6.1: Flow chart of trial period/phases

Trial phase	Description	Start (included)	End (excluded)
Screening phase	Screening	Date of informed consent	Date of start of first infusion of study drug (day 1).
Blinded Treatment phase	Randomised On-treatment period	Date of start of infusion of first study drug (Day 1)	Week 16 visit date + 1 day
Open label Treatment phase ¹	Re-allocation period (Either open label BI655130 or No treatment)	Week 16 visit date + 1 day	Date of EoS Participation visit + 1 day

Dates are defined individually per patient. If more than one date is associated with a specific visit, measurements associated with a specific date are assigned to a study analysis phase according to the rules specified in the table. An analysis phase will not extend beyond the start date of the following phase.

¹ Non-responders (i.e. EASI<75) at Week 16 will be re-allocated to BI655130 600mg IV open label and will continue in the trial until Week 44. Responders (EASI>=75) at Week 16 will be re-allocated to no treatment and will be observed until Week 28 or the day when they return to a 50% reduction in EASI score (EASI50) and start the treatment in the extension trial.

Patients who discontinue the treatment but will continue on trial visits will be included in analyses with the available data. For patients who discontinue trial prematurely only available data will be used in the analyses.

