For the final analysis of the trial to be performed once all patients have completed through the planned period, results will be summarized including the data from the reallocation period (Open-label Treatment phase). Results will be presented separately and in descriptive manner. The time windows for data presentation in this analysis are described in [Table 6.7: 1](#). In addition, analyses including the data from the double-blind period (initially used for the Primary Analysis) will be re-run after the final database lock.

To distinguish between assignment to trial periods/phases and AE assignments, please, refer to [Table 6.1:2](#).

Table 6.1: 2 AE assignment to analysis treatment groups

Randomised treatment	EASI75 response at Week 16	Open-label period	AE assignment to analysis treatment group
PLACEBO	Responder	No Treatment	AE that occurred between first randomised study drug intake and min[(EoS visit date), (last randomised study drug administration date + 112 days)] will be analysed under PLACEBO. AEs occurring later will be listed only.
PLACEBO	Non-Responder	BI 655130 Treatment	AE that occurred between first randomised study drug intake and Week 16 visit date (excluding) will be analysed under PLACEBO. AEs occurring later will be analysed under Open-label BI Treatment.
BI 655130	Responder	No Treatment	AE that occurred between first randomised study drug intake and min[(EoS visit date), (last randomised study drug administration date + 112 days)] will be analysed under BI 655130. AEs occurring later will be listed only.
BI 655130	Non-Responder	BI 655130 Treatment	AE that occurred between first randomised study drug intake and Week 16 visit date (excluding) will be analysed under BI 655130. AEs occurring later will be analysed under Open-label BI Treatment.

Treatment groups up to Week 16 will be labelled as follows:

- **"Speso 600 mg IV q4w"** (i.e., patients randomised to BI 655130 600 mg)
- **"Placebo"** (i.e., patients randomised to Placebo)
- **"Overall Total"** (across treatments: Placebo and BI 655130 600 mg), where appropriate.

Treatment groups for the efficacy analysis after week 16 will be labelled as follows:

- **"Open-label treatment: No Treatment"**
 - **"Placebo"** (i.e., patients randomised to Placebo in the double-blind treatment period and who did not receive an open-label BI 655130 treatment starting from Week 16 (V7))

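### A Responder who loses response at Week 20 or Week 24 and does not enter the extension leaves 50% or 25% of the 16-week residual effect period without active safety follow-up

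*Protocol*

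**What the plan says.** - **Residual effect period.** Protocol 7.3.4 defines it as "a period of 16 weeks after the last dose of trial medication" and assigns AEs with onset up to its end to the on-treatment period.
- **Last infusion of a Responder.** Protocol 6.2.2 gives the first infusion at V2 and continues: "Thereafter, patients will receive blinded trial drug at V4, V5 and V6". SAP 6.1 agrees, with dosing "at weeks 0, 4, 8, and 12". Responders receive nothing after that.
- **End of Study.** Flow Chart footnote 18 first says "For Responders (R) the EoS visit must be completed 16 weeks after last treatment", at the latest Week 28 (V10). Its next sentence says "Responders (R) may complete EOS at any point after V7 (Week 16) if the patient drops to an EASI 50 score" before the planned date. Section 3.1 goes further: such a patient has EoS straight away and is then offered the extension trial. Section 6.2.3 counts reaching that point as completing the re-allocation period.
- **Safety call.** Footnote 20: "Only Non-Responders not participating in the open label extension trial must complete an End of Study Safety Phone Call". Section 6.2.2.3 repeats the restriction. The pregnancy-status question (footnote 21 and Section 5.2.5.2) is asked at this call.
- **After EoS.** Under Section 5.2.5.2 "the investigator does not need to actively monitor the patient for new AEs". Cancer, related SAEs and related AESIs that the investigator happens to learn of are still reported, but not in the CRF.
- **Analysis.** SAP Table 6.1: 2 counts a Responder's AEs up to "min[(EoS visit date), (last randomised study drug administration date + 112 days" (closing brackets omitted), whichever comes first.

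**The concern.** The schedule is built so that every planned pathway reaches the end of the REP, with one exception: the Responder who loses response before Week 28 and does not go on to the extension. The extension is an offer, so a patient may decline it or not be eligible. That patient's exit counts as completion rather than withdrawal, active AE collection ends, and the call that would close the gap is reserved for Non-Responders.

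At stake is the safety information that the protocol itself treats as on-treatment. The number of patients with drug-related AEs is a secondary endpoint, and Section 2.1.1 calls safety and tolerability the main objective. Contraception is required for 16 weeks after the last infusion (Section 1.4), but no contact is planned in which these patients would be asked about pregnancy during the rest of that time.

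**Working it through.** **Inputs.** REP = 16 weeks = 112 days (Protocol 7.3.4; SAP Table 6.1: 2). Last Responder infusion: V6, Week 12, Day 85. Responder visits after Week 16: Weeks 20, 24 and 28, Days 141, 169 and 197 (Flow Chart; Section 3.1).

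**Reproducing the plan's own calendar.** Responders: 85 + 112 = Day 197 = Week 28 = V10. Non-Responders, last dosed at V10: 197 + 112 = Day 309 = Week 44. Both planned end points cover exactly one REP.

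**Early exit.** Days followed = EoS day − 85. Share without active follow-up = (112 − days followed) / 112.

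| EoS | Days followed | Days not followed | Share |
|---|---|---|---|
| Week 20 (Day 141) | 56 | 56 | 50% |
| Week 24 (Day 169) | 84 | 28 | 25% |
| Week 28 (Day 197) | 112 | 0 | 0% |
| Bound: day after Week 16 (Day 114) | 29 | 83 | 74% |

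In the limit at Day 113 the bound is 84/112 = 75%. With the ±3-day windows on both V6 and the exit visit, the Week 20 figure runs from 45% (144 − 82 = 62 days followed) to 55% (138 − 88 = 50 days). The Week 24 figure runs from 20% (90 days) to 30% (78 days).

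**Drug still present.** Section 1.2.3 gives a half-life of about 4 weeks. Assuming simple first-order decline, 25% of the level after the last dose remains 8 weeks later (Week 20) and 12.5% remains 12 weeks later (Week 24). This concerns only patients randomised to BI 655130.

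**Does another passage close the gap?** I found none.
- The telephone safety information in Section 4.2.1 is tied to protocol visits up to EoS.
- The early EoS 16 weeks after last treatment in footnote 18 is for premature treatment discontinuation.
- SAP Table 6.1: 1 describes the early-exit Responder only as someone who starts extension treatment, so one who does not has no described path.

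**Number affected.** The documents give none. Purely as an illustration, with 45 patients, 20–50% responding, 20–40% of those losing response before Week 28 and 10–30% of those not entering the extension, the range is 45 × 0.2 × 0.2 × 0.1 = 0.2 to 45 × 0.5 × 0.4 × 0.3 = 2.7 patients over both arms.

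**The case against.** Four arguments on the other side deserve weight.

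**The largest figure is a limiting case.** A reader might infer that about three quarters of the REP is routinely lost. That would need a patient with at least a 75% EASI reduction at Week 16 to fall to 50% almost at once and be seen outside the schedule, although Section 6.2.2.2 describes unscheduled visits during the treatment period. This stands: 50% and 25% are the figures at scheduled visits.

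**The patient is not wholly unobserved.** A reader might infer that all safety observation ends. It does not. AEs open at EoS are followed up, passive reporting continues (Section 5.2.5.2), known drug exposure in pregnancy must be reported, and SAP deviation G1.02 covers pregnancy or nursing up to 16 weeks after the last dose. This also stands. What is missing is active solicitation of new AEs and of pregnancy status.

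**No bias between arms follows.** A reader might reason that more Responders on BI 655130 means more AEs missed in that arm. But Table 6.1: 2 already stops a re-allocated Non-Responder's randomised-arm window at the Week 16 visit. A Responder leaving at Week 20 therefore contributes about 141 − 113 = 28 days more. SAP 7.8 also plans AE tables limited to first dose to Week 16, which early exit cannot affect. The documents do not support a bias claim.

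**The text can be read as keeping such patients in.** Footnote 18 is permissive, footnote 16 expects Responders at all visits to Week 28, and footnote 3 asks that patients who discontinue before their scheduled EoS be kept in the trial. This stands only in part. Section 3.1 is not permissive, and Section 6.2.3 treats the exit as completion, so the passages conflict and the gap is open on one of the two readings.

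**Conclusion.** The concern holds in a limited form. A Responder who falls to EASI 50 before Week 28 may (footnote 18) or must at once (Section 3.1) have EoS. If that happens at Week 20 or Week 24 and the patient does not enter the extension, 50% or 25% of the protocol's own 16-week REP has no active collection of AEs or pregnancy status.

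This rests on nominal visit days, a last infusion at Week 12 and the immediate-exit reading. The number of patients is not given and is likely to be small. The loss is of safety information in a few individuals, so this is a worthwhile, inexpensive improvement and not a threat to the trial's conclusions. The sponsor has already accepted the principle: Amendment 3 added the call so that Non-Responders outside the extension would have a safety assessment at the end of the residual period, and the same reason applies to this group.

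**What to change.** 1. **Reconcile the EoS wording.** Bring the two sentences of footnote 18 and Section 3.1 into agreement on whether the early exit is optional or immediate, and state what happens to a Responder who does not enter the extension. Which rule applies is for the sponsor to decide.
2. **Extend the existing call.** In footnote 20, Section 6.2.2.3 and the pregnancy text of Section 5.2.5.2, include any Responder whose EoS falls before the end of the REP and who does not enter the extension, with the call timed at the end of that patient's REP. If a Week 28 visit a few days early within its window is not meant to trigger a call, say so.
3. **Align the SAP.** Change Table 6.1: 2 so that AEs reported at that call, up to last dose + 112 days, are counted as Protocol 7.3.4 requires. At present the table cuts them off at EoS, while SAP Section 4 declares no change to the planned analysis.

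The cost is one extra telephone contact and a slightly later individual end of trial for a few patients, plus short edits to both documents. No dose, treatment or response rule changes.
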